14.5 Serious Adverse Event Reporting

All SAEs will be reported to Gradalis, Inc. within 24 hours of notification by the site through email or facsimile. This includes any death from any cause following procurement of the subject's tissue for tissue manufacture and for up to 30 days following the last dose of the protocol study agent (Vigil).

The site will supply as much information as is available at the time of the initial notification (study number, patient initials, patient study number, onset date, relationship, patient demographics, event, dosing regimen of study agent) to:

Gradalis, Inc.			
[name]			
[contact]			
Direct: [contact]	[contact]		

Gradalis, Inc. will report adverse events to the FDA in compliance with 21 CFR 312.32.

15.0 PATIENT COMPLETION AND WITHDRAWAL

15.1 Indication for Taking Patients Off Study

The Investigator must notify the sponsor at any time following discontinuation of a patient on study for the occurrence of a serious or unexpected AE associated with the use of the study medication.

16.0 STATISTICAL CONSIDERATIONS

16.1 Sample Size Justification

This is an open label randomized controlled Phase III clinical trial. Information concerning the predicted survival of the control group is limited, based on rarity of disease and few published reports. However expert advisors in the EWS field estimate a conservative one-year survival rate of 25% in the chemotherapy control group. The one-year survival rate of 60% in the Vigil treated group is estimated from EWS patients treated on the Vigil phase 1 protocol. These estimates correspond to a hazard ratio (HR) of 0.383 favoring Vigil over control.

Assuming 1:1 randomization and the use of a two-sided log rank test at the alpha=0.0476 level of significance, 67 events will provide 90% power to detect an PFS HR of 0.45. Assuming a Group B (control group) median PFS of 6 months, a one-year accrual period, and a six-month follow-up period after randomization of the last subject, it is estimated that the total sample size (number of subjects) required to achieve 67 events is 114 (57 patients in each arm).

An unblinded interim analysis will be conducted by an independent data monitoring committee (IDMC) when 40 PFS events have occurred. Based on the results of this interim analysis, the planned sample size may be increased to 120 events. If the sample size is increased to 120 events, then the study will have approximately 90% power to detect a true HR of 0.55. Note that if the sample size is increased to 120 events, then the accrual period will be extended to 24 months, with a 6-month follow-up period after randomization of the last patient. Under these assumptions, it is estimated that approximately 164 patients will need to be randomized in order to achieve 120 events. Section 16.6 provides further details.

16.2 Definition of Progression Free Survival (PFS)

- Progression free survival (PFS) is defined as the time from randomization to the event of disease recurrence/progression or death due to any cause.
- Radiographic disease recurrence/progression will be assessed using the RECIST 1.1 criteria. If the disease recurrence/progression assessment involves more than one date, the earliest date will be used as the event date.
- Patients who are alive and recurrence free at the time of analysis data cut-off, or who terminate the study for reasons other than disease progression or death, or who receive non-protocol treatment for Ewing's Sarcoma, will be censored on the last assessment date at which a RECIST 1.1 evaluation of disease status was made.
- Patients missing baseline disease assessment will be censored at date of randomization.
- For equivocal findings of recurrence (e.g., very small and uncertain new lesions; cystic changes or necrosis in existing lesions), treatment may continue until the next scheduled assessment. If recurrence is confirmed at the next scheduled assessment, the date of recurrence should be the earlier date when recurrence was suspected.

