9.0 SCHEDULE OF ASSESSMENTS

Pre-study Assessments / Surgery Pre-Screening

The following evaluations will be performed within 4 weeks of tumor procurement (unless otherwise specified):

- 1. A signed Informed Consent Form for tissue harvest must be obtained.
- 2. It has been confirmed that the subject meets all tissue procurement inclusion criteria and none of the exclusion criteria.
- 3. A complete medical history must be obtained.
- 4. A physical examination must be obtained.

- 5. A complete blood count (CBC) with differential and platelet count must be performed. (HIV and hepatitis testing is not required if the subject has no medical history of HIV).
- 6. Routine pre-operative serum chemistries (including, but not limited to creatinine, total bilirubin, alkaline phosphatase, and aspartate transaminase (AST) and/or alanine transaminase (ALT).
- 7. Blood collection for immune function analysis will be obtained at tissue harvest. (≤1 week of tissue procurement)
- 8. Plasma collection for immune function analysis (ctDNA) (≤1 week of tissue procurement)

Screening Assessments / Protocol Screening

The following evaluations will be performed on all subjects within 2 weeks of Cycle 1 (unless otherwise specified):

- 1. A signed protocol specific Informed Consent Form must be obtained.
- 2. It has been confirmed that the subject meets all inclusion criteria and none of the exclusion criteria.
- 3. A physical examination (including vital signs, height, temperature and body weight) must be obtained.
- 4. Assessment of concomitant medications
- 5. Assessment of PS on the Karnofsky or Lansky scale (see Appendix A) must be obtained.
- 6. Radiological assessment of disease status with computed tomography (CT) chest /abdomen/pelvis (magnetic resonance imaging (MRI) abd/pelvis may be substituted for CT abd/pelvis) within 4 weeks of Cycle 1. The methods used for prestudy assessments (e.g., CT or MRI) should be used throughout the study. If possible, the same equipment should be used each time. Radiographic assessments must be from after the tissue harvest for vaccine manufacture to ensure true baseline disease status is captured. Images must be uploaded into WorldPro or submitted to WorldCare.
- 7. A complete blood count (CBC) with differential and platelet count must be performed. (HIV and hepatitis testing is not required if the subject has no medical history of HIV).

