16.3 Analysis Populations

The intent-to-treat (ITT) population will include all randomized subjects. All efficacy analyses will be completed in the ITT population.

The Safety population will include all patients who receive study treatment and patients will be analyzed according to actual treatment received. All safety analyses will be completed in the Safety population.

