16.4.3 Sensitivity Analyses of the Primary Endpoint

Five sensitivity analyses of the primary endpoint will be conducted using each of the following modifications to the definition of PFS:

- If the disease recurrence/progression assessment involves more than one date, the latest date will be used as the event date.
- If disease recurrence or death occurs right after missing data for a scheduled radiographic disease assessment (including missing the assessment or assessment results in an unevaluable status for overall response per RECIST 1.1), the patient will be censored at the date of the last radiographic disease assessment.
- If a patient receives non-protocol treatment for Ewing's Sarcoma, the patient will be treated as having progression at the date of the last radiographic disease assessment.
- Patients missing baseline disease assessment will be treating as had having progression at the date of randomization.
- For equivocal findings of recurrence (e.g., very small and uncertain new lesions; cystic changes or necrosis in existing lesions) for whom treatment continues until the next scheduled assessment, and if recurrence is confirmed at the next scheduled assessment, the date of recurrence should be the date when recurrence was confirmed.

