8.1 Efficacy Analyses

8.1.1 Primary Efficacy Analysis

The primary endpoint of PFS is the time from randomization to progression according to RECIST version 1.1 or death. The distributions of PFS in the two arms will be compared using a two-sided log-rank test at the alpha=0.0476 level of significance.

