8.1.3 Sensitivity Analyses of the Primary Endpoint

Five sensitivity analyses of the primary endpoint will be conducted using each of the following modifications to the definition of PFS:

- If the disease recurrence/progression assessment involves more than one date, the latest date will be used as the event date.
- If disease recurrence or death occurs right after missing data for a scheduled radiographic disease assessment (including missing the assessment or assessment results in an unevaluable status for overall response per RECIST 1.1), the patient will be censored at the date of the last radiographic disease assessment.
- If a patient receives non-protocol treatment for Ewing's Sarcoma, the patient will be treated as having progression at the date of the last radiographic disease assessment.
- Patients missing baseline disease assessment will be treated as having progression at the date of randomization.
- For equivocal findings of recurrence (e.g., very small and uncertain new lesions; cystic changes or necrosis in existing lesions) for whom treatment continues until the next scheduled assessment, and if recurrence is confirmed at the next scheduled assessment, the date of recurrence should be the earlier date when recurrence was suspected.

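### PFS counts death from any cause, yet a subject with no baseline disease assessment is censored at randomisation with no exception for death

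*Protocol*

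**What the plan says.** Protocol 16.2 opens with the event definition: "Progression free survival (PFS) is defined as the time from randomization to the event of disease recurrence/progression or death due to any cause". The fourth bullet of the same list reads "Patients missing baseline disease assessment will be censored at date of randomization". SAP 7.1 carries both statements unchanged. The endpoint restatement in SAP 8.1.1, "The primary endpoint of PFS is the time from randomization to progression according to RECIST version 1.1 or death", adds no rule for a death without a baseline assessment, and neither do Protocol 16.4.1 or SAP 4.1.

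The analysis set is all randomised subjects: "The intent-to-treat (ITT) population will include all randomized subjects. All efficacy analyses will be completed in the ITT population".

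One of the five sensitivity analyses addresses this group. In Protocol 16.4.3 it reads "Patients missing baseline disease assessment will be treating as had having progression at the date of randomization", and in SAP 8.1.3 "Patients missing baseline disease assessment will be treated as having progression at the date of randomization".

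The baseline scan is a screening procedure in Protocol 9.0, timed "may be substituted for CT abd/pelvis) within 4 weeks of Cycle 1". SAP 12.1.1 ties it to registration instead. A completed scan is not among the enrolment criteria in Protocol 6.4 and 6.5. The Long Term Follow Up part of Protocol 9.0 asks subjects who are randomised but never treated to allow quarterly survival follow-up.

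**The concern.** A baseline scan is needed to judge progression by RECIST. It is not needed to know that a subject has died, or when. Read literally, the fourth bullet overrides the first for a subject who lacks the scan and dies, and no text elsewhere restores the death. The plan provides for collecting survival status on untreated subjects, so it could record such a death and then leave it out of the primary endpoint.

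The trial is open label, and subjects who leave between randomisation and Cycle 1 need not be alike in the two arms. If more deaths are lost from one arm, the PFS comparison shifts in that arm's favour. If the losses are balanced, the cost is events and power.

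**Working it through.** **Step 1. Set the rules side by side for a subject with no baseline assessment who dies on day *t*.**

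| Rule | Time used | Status used |
|---|---|---|
| PFS definition, first bullet (Protocol 16.2, SAP 7.1) | *t* | event |
| Missing-baseline bullet (same lists) | 0 | censored |
| Fourth sensitivity analysis (Protocol 16.4.3, SAP 8.1.3) | 0 | event |

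Neither planned analysis uses *t*. The sensitivity analysis also gives a day-0 event to subjects in this group who neither progressed nor died.

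**Step 2. Reproduce the design.** Inputs from Protocol 16.1: HR 0.45, two-sided alpha 0.0476, power 90%, 1:1 allocation, control median 6 months, 12 months' accrual, 6 months' follow-up.

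- Events (Schoenfeld): 4(1.981 + 1.282)² / (ln 0.45)² = 66.8, so 67. This matches the plan.
- Event probability with hazard λ: 1 − [exp(−6λ) − exp(−18λ)] / (12λ). With λ = ln 2/6 this is 0.729 (control), and with 0.45λ it is 0.455 (Vigil). Expected events at 114 subjects: 57 × (0.729 + 0.455) = 67.5. This also matches.

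**Step 3. Effect of one dropped death.** A very early death in one arm of a 1:1 trial changes observed minus expected by about 0.5. The log-rank variance is about 67/4 = 16.75. The shift in Z is 0.5/√16.75 = 0.12. For scale, the critical value is 1.98 and the expected Z at HR 0.45 is 0.7985 × √16.75 = 3.27.

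The shift shrinks with time to death. Simulating the design at true HR 0.45 or 1.0, dropping one subject moves Z by 0.10 to 0.14 for a death at 0.5 months, 0.03 to 0.07 at 6 months, and 0.03 or less at 9 months. Losing a Vigil death favours Vigil; losing a control death works against it.

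**Step 4. Power if missingness is balanced and unrelated to risk.** The documents give no missing rate, so 2% to 10% is assumed. Power is Φ(0.7985 × √events / 2 − 1.981) at the planned calendar cut-off.

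| Missing (assumed) | Subjects | PFS events lost | Events left | Power |
|---|---|---|---|---|
| 0% | 0 | 0 | 67.5 | 90.3% |
| 2% | about 2 | 1.4 | 66.2 | 89.7% |
| 5% | about 6 | 3.4 | 64.2 | 88.8% |
| 10% | about 11 | 6.8 | 60.8 | 87.1% |

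These losses count progressions as well as deaths. The deaths, which are all the fix can recover, are a subset.

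**Step 5. One-sided case.** Illustrative simulation, 4,000 runs, true HR 0.45, with 6 of 114 subjects missing baseline and at twice the hazard (both assumed):

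| All 6 in | HR, real events counted | HR, primary rule | HR, sensitivity rule |
|---|---|---|---|
| Vigil | 0.48 | 0.46 | 0.58 |
| Control | 0.41 | 0.44 | 0.39 |

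The two planned analyses bracket the value obtained with real event dates, but neither gives it. The sensitivity rule overshoots, markedly so when the missing scans are in the Vigil arm.

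**The case against.** The strongest reply is that the rule may never be used. The scan is a screening procedure for every subject. Eligibility is reconfirmed, and registration goes to the medical monitor, before the randomisation result is released (Protocol 8.1). Performance status must be at least 80% (Protocol 6.4). A subject who declines between procurement and registration should fail screening and never enter the ITT set, so the exposed interval is mainly the short one from randomisation to Cycle 1. The group already has its own sensitivity analysis, and the deaths still count in overall survival. All of this stands, and it limits the size of the point. It does not reconcile the two bullets.

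Two stronger readings are tempting and should not be drawn.

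- A reader might infer that a treated subject whose only scan predates tissue harvest is also censored at day 0, because Protocol 9.0 says "Radiographic assessments must be from after the tissue harvest for vaccine manufacture". No text says that such a scan counts as missing. SAP 10.3 defines baseline as the last non-missing assessment before first dosing, and under that definition the earlier scan would serve. Failing the timing requirement is a deviation, not a missing baseline.
- A reader might multiply 0.12 by two to four deaths and expect a Z shift of 0.24 to 0.49. That needs two to four subjects without a scan, all of whom die very early and all in one arm. Nothing in the documents makes this likely, and entry requires an estimated survival of at least 6 months (Protocol 6.2).

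A further objection concerns the remedy. Simply adding an exception for any death would let a death many months later, after progression nobody could assess, set the PFS date. It would also make membership of the risk set depend on a remote outcome. That objection is sound, and it is why the fix needs a time window.

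**Conclusion.** The concern holds as a gap in the primary endpoint definition. As written, both documents censor at randomisation a subject who lacks a baseline assessment and dies, contrary to their own definition of PFS, and no planned PFS analysis uses the death date. The text does not show that deaths will in fact be lost, or that the result will lean towards Vigil: the number affected is not given and may be zero to a few, and the direction depends on the arm.

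The effect is about 0.12 on Z per very early death in one arm at 67 events, and less for later deaths. If missingness is balanced, 5% missing costs about 1.5 points of power (90.3% to 88.8%) at the planned calendar cut-off. The missing rates and the doubled hazard are assumptions. The point merits correction because the contradiction is plain and the repair is cheap, not because a large bias is expected.

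**What to change.** Amend the bullet in Protocol 16.2 and SAP 7.1 to read: *Subjects with no baseline disease assessment are censored at randomisation, unless they die within a pre-specified window after randomisation (for example two scheduled scan intervals, 12 weeks plus the visit window), in which case death is a PFS event on its date.*

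State how this ranks against the bullet that censors for non-protocol treatment. Otherwise an untreated subject who takes other therapy and then dies inside the window falls under two conflicting rules.

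In the fourth sensitivity analysis (Protocol 16.4.3, SAP 8.1.3), use the actual death date for subjects who die within the window, and progression at randomisation for the rest of the group.

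Make the change before the unblinded interim at 40 events; a later change to the primary event rule could look driven by the data.

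Cost: one amended sentence per document, a precedence statement and a matching edit to the sensitivity analysis. Death dates are already needed for overall survival, and the design stays at 67 events and 114 subjects. The window length is a convention, and a few later deaths without a baseline scan stay censored. Within the window, being at risk still depends on having died; the limit contains that weakness but does not remove it.

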16.3 Analysis Populations

The intent-to-treat (ITT) population will include all randomized subjects. All efficacy analyses will be completed in the ITT population.

The Safety population will include all patients who receive study treatment and patients will be analyzed according to actual treatment received. All safety analyses will be completed in the Safety population.

16.4 Efficacy Analyses

16.4.1 Primary Efficacy Analysis

The primary endpoint of PFS is the time from randomization to progression according to RECIST version 1.1 or death. The distributions of PFS in the two arms will be compared using a two-sided log-rank test at the alpha=0.0476 level of significance

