1.2 Relapsed and Refractory Ewing's sarcoma

Thirty to forty percent (30-40%) of Ewing's sarcoma patients who present with localized disease, and 60-80% presenting with primary metastatic disease, will experience relapse or progression at a median time to relapse of 1.3 years (Ozaki, Hillmann et al. 1996, Bacci, Picci et al. 1998, Klingebiel, Pertl et al. 1998, Leavey and Collier 2008, Stahl, Ranft et al. 2011). Presentation with localized disease is associated with a 6-year event free survival (EFS) rate of 69% and overall survival (OS) rate of 72% (Leavey, Mascarenhas et al. 2008). If patients present with metastatic disease at diagnosis, the 6-year event free survival in this analysis significantly deteriorated to 28% with OS 29% (Guerney, Swensen et al. 1999, Miser, Goldsby et al. 2007, Leavey, Mascarenhas et al. 2008). Other reports have shown worse overall survival in patients who relapse with a marked reduction in overall survival of only 12% at 5 years, and 19% at 2 years (Leavey, Mascarenhas et al. 2008). Factors like site of recurrence (localized, metastatic, combined localized and metastatic) and time to relapse (<2 years or >2 years) play important prognostic factors for survival in recurrent Ewing's sarcoma (Table 1). For relapses that occur

within the first 2 years after initial diagnosis, which make up 72% of relapses (Stahl, Ranft et al. 2011), the 2-year OS was 7% (Shankar, Ashley et al. 2003), 5-year EFS was 5% (Bacci, Ferrari et al. 2003), and 5-year OS was 7% (Stahl, Ranft et al. 2011). In addition, response status to frontline therapy like recurrence (initial response followed by relapse) versus refractory (disease progression on first line regimen) appear to correlate with clinical outcome, while the survival rate is dismal for patients that do not respond to frontline therapy (Casey, Wexler et al. 2009).

PI	Number Patients	Primary Metastatic Disease at Diagnosis	5-year Overall Survival After First Relapse	5-year OS: Relapse < 2 years from Initial Diagnosis	5-year OS: Relapse ≥ 2 years from Initial Diagnosis
Stahl 2011	714	35%	13.0%	7.0%	29.0%
Leavey 2008	262	46%	12.0%	7.0%	30.0%
Bacci 2003	195	0%	13.8%	2.5%	14.3%
Rodriguez- Galindo 2002	71	42%	23.7%	5.0%	34.9%
Shankar 2003	64	0%	10.0%	7.0%	45.0%
Barker 2005	55	38%	23.0%	12.0%	48.0%
McTiernan 2006	114	47%	15.2%	6.7%*	31.6%
*Relapse free interval defined as < or ≥ 18 months.					

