5.0 STUDY DESIGN

This is a multicenter, 1:1 randomized Phase III study of intradermal autologous Vigil immunotherapy (1.0 x 10⁶ cells/injection; minimum of 4 to a maximum of 12 administrations) in combination with irinotecan and temozolomide in subjects with metastatic Ewing's Sarcoma Family of Tumors (ESFT) refractory/intolerant or recurrent to 1 prior line of chemotherapy. Participants undergoing a standard surgical procedure (e.g., tumor biopsy or palliative resection) may have tumor tissue harvested for manufacture of investigational product

Subjects meeting eligibility criteria including manufacture of a minimum of 4 immunotherapy doses of Vigil will be randomized to receive either:

Group A

- (i) oral temozolomide 100 mg/m² daily (Days 1 5, total dose 500 mg/m²/cycle),
- (ii) oral irinotecan 50 mg/m² daily (Days 1 5, total dose 250mg/m²/cycle), and
- (iii) Vigil 1.0×10^6 cells/injection, intradermally on Day 15.

OR

Group B

- (i) oral temozolomide 100 mg/m² daily (Days 1 5, total dose 500 mg/m²/cycle), and
- (ii) oral irinotecan 50 mg/m² daily (Days 1 5, total dose 250mg/m²/cycle).

If chemotherapy study drugs cannot be administered orally (i.e. size of capsule, nausea, etc.) it is the physician's discretion to request intravenous administration of temozolomide at 100 mg/m² daily and/or irinotecan 20 mg/m² daily intravenously.

One cycle = 21 days. Screening for the main portion of the study may occur as early as one week but no later than 8 weeks following tumor procurement. Vigil is typically released approximately 3 weeks after the completion of the two-day manufacturing process. At the time of data analysis the subjects will be stratified by initial response to frontline treatment (recurrent versus refractory (progressive)).

Participants will be managed in an outpatient setting. Hematologic function, liver enzymes, renal function and electrolytes will be monitored. Blood for immune function analyses including IFNγ-ELISPOT analysis of cytotoxic T cell response to autologous tumor antigens will be collected at tissue procurement, post-procurement screening and Day 1 (prior to chemotherapy administration) at Cycles 2, 4, and 6, end of treatment (EOT), 3 months after EOT, and every 6

months thereafter. Blood for exploratory ctDNA analysis will be collected at tissue procurement, prior to chemotherapy administration at baseline, prior to chemotherapy administration on Day 1 of Cycles 2, 3, 4, and 6, and EOT.

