16.4.5 Subgroup Analyses of the Primary (PFS) and Key Secondary Endpoints (OS, ORR)

Subgroup analyses will be conducted in the following subsets of the ITT population:

- Race / ethnicity
- Study site / region
- Age group (<15 years (low), ≥15 years (high))
- Gender
- Number of doses received (≤median number of doses administered, >median number of doses administered)
- Number of lines of prior treatments including chemotherapy and radiation
- At time of diagnosis: localized vs. metastatic disease
- At time of diagnosis: skeletal vs. extraskeletal
- At time of diagnosis: tumor volume/burden (<100ml or 8cm vs >100ml or 8cm)
- Response to frontline therapy (CR vs. PR vs. SD vs. progressive disease)
- Time to first recurrence: <2 years, > 2 years

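### Time to first relapse, which the protocol itself calls prognostic, is used only for a subgroup analysis and not in the primary PFS log-rank test, at a small, conditional cost in power and robustness

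*Protocol*

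**What the plan says.** Protocol 1.2 states that site of recurrence and "time to relapse (<2 years or >2 years) play important prognostic factors for survival" in recurrent Ewing's sarcoma. Table 1 supports this with seven series (one cut at 18 months instead of 2 years). The same section puts 72% of relapses within 2 years of diagnosis.

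The factor then appears once in the analysis plan, as a subgroup in Protocol 16.4.5 and SAP 8.1.5: "Time to first recurrence: <2 years, > 2 years". The primary test is given in Protocol 16.4.1, and in the same terms in SAP 8.1.1: "The distributions of PFS in the two arms will be compared using a two-sided log-rank test". No stratum or covariate is named. The OS log-rank tests in Protocol 16.4.2 and SAP 8.1.2 name none either. SAP 10.1.2 mentions a Cox model without covariates. The five PFS sensitivity analyses vary event and censoring rules only.

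The design sections (Protocol Synopsis and 5.0, SAP 5.0) announce one stratification: "At the time of data analysis the subjects will be stratified by initial response to frontline treatment", meaning recurrent versus refractory. The sections that define the tests do not repeat it. Randomisation is described as 1:1, and the text gives no strata. The baseline variables listed in SAP 11.2 do not include time to relapse.

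**The concern.** A log-rank test that ignores a strong prognostic factor estimates an HR pulled towards 1 relative to the effect within strata, and it carries any chance imbalance on that factor straight into the estimate. With 57 subjects per arm such imbalances are not rare. The interim rules in Protocol 16.6 act on the observed HR at 0.43, 0.51 and 0.61. These bands are narrow: ln(0.51/0.43) = 0.17 and ln(0.61/0.51) = 0.18 on the log scale. The value is known at entry and is already needed for the subgroup analysis. Splitting the result by subgroup does not adjust the overall comparison.

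**Working it through.** **1. The plan's own figures.** Protocol 16.1 states that "67 events will provide 90% power to detect an PFS HR of 0.45", with two-sided alpha 0.0476.
- Schoenfeld: d = 4(z_α/2 + z_β)² / (ln HR)² = 4(1.981 + 1.282)² / (0.7985)² = 66.8, so 67 events. Power at 67 events is 90.1%.
- Sample size: "Assuming a Group B (control group) median PFS of 6 months, a one-year accrual period, and a six-month follow-up period" gives, for exponential PFS and uniform accrual, event probabilities of 1 − (0.500 − 0.125)/1.386 = 0.730 (control) and 1 − (0.732 − 0.392)/0.624 = 0.455 (Vigil). The mean is 0.592, and 67/0.592 = 113.1 against 114 stated. Both figures reproduce.

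**2. Size of the factor.** Under proportional hazards, the early:late hazard ratio is ln(early OS)/ln(late OS). The largest Table 1 series (n=714) gives ln(0.07)/ln(0.29) = 2.659/1.238 = 2.15. The seven rows range from 1.90 to 3.33. These are OS figures. The documents give no PFS split, so applying the ratio to PFS is an assumption, and ratios from 1.0 to 3.33 were examined.

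**3. Power by simulation.** 114 subjects, 12-month uniform accrual, analysis at the 67th event, 72% early relapse, control mixture median held at 6 months, HR 0.45 within strata, no interim look, 20,000 trials per row:

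| Early:late PFS ratio (assumed) | Unstratified | Stratified by time to relapse | Difference (points) |
|---|---|---|---|
| 1.0 | 89.5% | 88.9% | −0.6 |
| 1.25 | 89.3% | 88.8% | −0.5 |
| 1.5 | 88.3% | 88.6% | +0.3 |
| 1.9 | 87.3% | 88.4% | +1.1 |
| 2.15 | 86.5% | 88.6% | +2.0 |
| 3.33 | 83.6% | 88.9% | +5.4 |

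A separate run of 8,000 trials agrees: 87.0% versus 88.6% at 2.15, 88.2% versus 88.5% at 1.5, and 89.2% versus 88.7% with no effect.

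**4. How to form the strata.** The documents give no refractory share, so 30% was assumed.
- Three strata (refractory, early relapse, late relapse): 87.1% unstratified versus 87.9% stratified at 2.15, a loss of about 0.5 point at 1.5, and a loss of 1.2 points with no effect.
- Two strata (relapse at 2 years or later versus all others): stratified power of 88.8%, 88.9% and 89.0% at ratios 2.15, 1.5 and 1.0.

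Two levels therefore do better than three.

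**5. Chance imbalance.** Under simple 1:1 randomisation, the SD of the difference in early-relapse share is √(2 × 0.72 × 0.28/57) = 0.084. A gap of at least 10 points means at least 6 subjects (6/57 = 10.5 points). With continuity correction, z = (5.5/57)/0.084 = 1.15, a two-sided probability of about 25%; simulation also gives about 25%. For 15 points or more it is about 7.5%. A 10-point gap multiplies the unadjusted HR by roughly exp(0.10 × ln 2.15) = 1.08, in either direction. In the 4.5% of trials with 14 to 19 points more early relapse in the Vigil arm, at a ratio of 2.15, the mean estimated HR is 0.51 unstratified versus 0.44 stratified, and power is 77% versus 89%.

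**6. Type I error.** Simulated rates were 4.3% to 5.3% (5,000 trials per scenario) against the nominal 4.76%, so there is no inflation.

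**The case against.** The strongest reply is that the gain is small and rests on an OS ratio from historical series. Entry requires a performance score of at least 80%, estimated survival of at least 6 months and procurable soft tissue or pleural fluid, so the ratio in this trial may be smaller. That stands. At 1.5 or below there is no material gain.

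A reader might infer that the trial falls short of its planned 90% power. The documents do not support this. Protocol 16.1 most naturally treats 0.45 as the overall HR for an ordinary log-rank test. On that reading the planned test is not underpowered for this reason, and stratifying would be an extra gain. The shortfall arises only if 0.45 is the effect within strata, and then the stratified test does not quite reach 90% either.

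The announced recurrent/refractory stratification may also help. At 2.15, with an assumed 30% refractory who all share the early-relapse hazard, it recovers nothing (86.3%). If refractory subjects did worse (assumed ratio 3.5), stratifying by that factor alone gives 87.3%, against 88.1% with three strata. It may therefore do part of the work, but only if it is written into the test.

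Other strong readings also fail:
- An imbalance of 10 points or more is possible (25%), not likely; the median absolute imbalance is about 5 points.
- Section 1.2 does not rank time to relapse as the strongest factor. It names site of recurrence beside it and discusses response to frontline therapy.
- An imbalance would not be hidden, since subgroup results by arm would ordinarily show the counts.
- The text describes no randomisation strata. That is less than proof that none are used.

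**Conclusion.** The point holds as one of efficiency and robustness, not of validity. The plan names a prognostic factor, collects it, and leaves it out of the primary test. The stratification it does announce is missing from the sections that define the tests. If the Table 1 OS ratio of about 2.15 applied to PFS and HR 0.45 held within strata, power would be about 87% unstratified and about 88.5-89% stratified. The difference is about nil at 1.5 and about minus 0.5 point with no effect. The firmer argument is protection against an unlucky allocation: about one trial in four would have a gap of 10 points or more, worth about 8% on the unadjusted HR at a ratio of 2.15. A claim that the unstratified test is invalid, or that its error rate is inflated, would be wrong.

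**What to change.** Before any unblinded data are seen:
- Amend Protocol 16.4.1 and 16.4.2 and SAP 8.1.1 and 8.1.2 so that the PFS and OS log-rank tests, and the Cox model giving the HR, are stratified by time to first relapse in two levels: 2 years or later from diagnosis, versus all others. Place refractory subjects in the second level.
- Reconcile this with the recurrent/refractory stratification in the Protocol Synopsis, Protocol 5.0 and SAP 5.0, so that every section names the same strata.
- Keep the unstratified log-rank test as a supportive analysis.
- Add time to first relapse to the baseline table in SAP 11.2.

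The randomisation need not change. The cost is a formal amendment with IRB approval under Protocol 11.5, because the primary test is defined in the protocol, and up to about 0.5 point of power if the factor has no effect on PFS. The variable is already needed for the planned subgroup analysis.
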